Study Title: A Multicenter, 2 Part Study to Assess the Efficacy and Safety of Acthar Gel in Subjects With Rheumatoid Arthritis With Persistently Active Disease

Protocol Number: MNK14294063

Type: Phase 4 (US)/Phase 2 (all other countries)

Condition/Disease:

Rheumatoid Arthritis

- The Per-Protocol Population will include the subset of the mITT population who complete the study as per protocol.
- The Safety Population will include all enrolled subjects who receive 1 or more doses of study drug.

Sample Size

It is expected that 360 subjects will be screened and a total of 232 subjects will be enrolled in this study. It is estimated that 55% of subjects will either drop out before Week 12 or will not achieve LDA by Week 12. The remaining 45% of subjects will have achieved LDA after 12 weeks of treatment with Acthar and will be randomized into 2 treatment groups in Part 2 of the study. Based on results from previous studies, it is estimated that 80% of the Acthar group and 50% of the placebo group will maintain LDA after the 12 additional weeks of treatment. Assuming that 52 subjects per group (104 subjects total) will complete Part 2, and based on the use of a 2-sided, 2-sample comparison of proportions at the alpha = 0.05 level of significance, there will be 90% of power to detect a difference in the 2 treatment groups.

Efficacy

For the primary endpoint, the proportion of subjects with LDA at Week 12 along with a 2-sided 95% confidence interval will be provided. The lower bound of the 95% confidence interval will be used to evaluate the response rate. The study will be deemed successful if the lower bound of the 95% confidence interval is $\geq 10\%$.

For the secondary endpoints, the proportions of subjects who maintain LDA in Part 2 for the 2 treatment groups will be compared using a 2-sided Pearson's chi-square test at a significance level of 0.05. The time to disease activity flare in Part 2 will be analyzed using log-rank test. The proportion of subjects with CDAI ≤ 10 at Week 12 and the proportion of subjects who meet criteria for ACR 20 at Week 12 will be analyzed using the same method as that for the primary endpoint.

For the exploratory endpoints,

[Redacted text block]

[figure not shown]
Safety

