9.3 Dosage and Administration

Investigational medicinal product (IMP) or study drug will be used to denote active drug (Acthar) and/or matching placebo.

Following a screening period of up to 28 days, subjects with RA with persistently active disease will receive open label treatment with 1 mL (80 U) of Acthar SC 2x/week for 12 weeks in Part 1 (Open Label Period) of the study.

After 12 weeks of treatment with Acthar, subjects will be evaluated for treatment response using the DAS28 - ESR. Subjects who have achieved LDA, defined as DAS28-ESR < 3.2, will enter a double-blind randomized maintenance period (Part 2, Randomized Maintenance Period) and receive either Acthar 1 mL (80 U) SC or matching placebo SC 2x/week for an additional 12 weeks. Subjects who do not achieve LDA will be discontinued from study participation.

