11 STUDY DESIGN

11.1 Description

This is a multicenter, multiple dose study to examine the effect of Acthar in adult subjects with RA with persistently active disease. Approximately 232 subjects will be enrolled.

During the first part of the study (Part 1-Open Label Period) all enrolled subjects will be treated with Acthar 1 mL (80 U) SC 2x/week for 12 weeks to assess the proportion of subjects who achieve LDA.

After 12 weeks of Acthar treatment, subjects who have achieved LDA (defined as DAS28-ESR < 3.2) will enter a double-blind randomized maintenance period (Part 2-Randomized Maintenance Period) and will be randomized in a 1:1 ratio into 2 groups:

- Group 1: Acthar 1 mL (80 U) SC 2x/week for an additional 12 weeks.
- Group 2: Placebo 1 mL SC 2x/week for an additional 12 weeks.

Subjects who do not achieve LDA at Week 12 will be discontinued from the study.

Subjects who experience a flare in disease activity will be discontinued from the study. Flare or worsening of disease activity is defined as:

- **Weeks 0 to 11:** DAS28-ESR ≥ 3.2 and increase of > 0.6 from the Week 0 assessment sustained over 2 consecutive study visits; **or** DAS28-ESR ≥ 3.2 and increased of > 1 from the Week 0 assessment at a single visit.
- **Weeks 13 to 23:** DAS28-ESR < 3.2 and increase of 1.2 from the Week 12 assessment; **or** DAS28-ESR ≥ 3.2 and increased of > 0.6 from the Week 12 assessment sustained over 2 consecutive study visits; **or** DAS28-ESR ≥ 3.2 and increase of > 1 from the Week 12 assessment at a single visit ([van der Maas, 2013](#)).

All subjects will have a Follow-up Visit 28 (± 2) days after their last dose of study drug.

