14.4 Week 12 (\pm 2 days) Procedures/Assessments

- Efficacy Questionnaires.
- WPAI.
- Current medical condition review.
- Limited physical examination.
- 28 Joint Count.
- Weight.
- Vital signs.
- Clinical laboratory tests.
- HbA1c.
- ESR and CRP.
- ██████████.
- ██████████/urine creatinine samples.
- Urine pregnancy test.
- Hospital admissions, ED visits, and nonstudy outpatient visits.
- Subject diary review.
- Study drug accountability.
- Contact IXRS and confirm disease activity eligibility.
- Dispense study drug kits (if appropriate).
- Adverse events and concomitant medications.

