15.1 Methods of Assigning Subjects to Treatment Groups

The investigator or designee will contact IXRS to register subjects at screening. The subject's identification (ID) number will be determined by the IXRS and will be used to identify the subjects for the duration of the study within all systems and documentation. Subject identification numbers will consist of 7 digits: [REDACTED]

A subject ID number will not be assigned to more than 1 subject. If a subject is not eligible to receive treatment, or should a subject discontinue from the study, the subject ID number cannot be reassigned to another subject.

In the event that a subject is rescreened within the screening window, they do not need a new subject ID number. At Baseline, qualified subjects who meet all of the eligibility criteria will be enrolled into the study.

The investigator or designee must contact the IXRS to report subjects as a screen failure if the subject does not meet eligibility criteria predose.

The investigator or designee must contact IXRS to record each subject visit, to receive the study drug kit assignments, and to report any subject status changes. At visits where it is required, components of the DAS28-ESR (swollen joint count, tender joint count, ESR, General Health VAS) will be entered at into IXRS and the DAS28-ESR will be calculated.

The investigator must maintain a subject master log linking the subject ID to the subject's name. The investigator must follow all applicable privacy laws in order to protect a subject's privacy and confidentiality. Information that could identify a subject will be masked on material received by the sponsor.

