15.3.1 Treatment Discontinuation

Treatment with study drug should be discontinued if any of the following occur:

- Development of accelerated hypertension (defined as systolic blood pressure ≥ 180 *and* diastolic blood pressure ≥ 100 mm Hg) that cannot be managed by the adjustment of concomitant medications such as antihypertensive medications.
- Development of congestive heart failure that cannot be managed by the adjustment of concomitant medications such as diuretics and antihypertensive medications.
- Development of diabetic signs/symptoms (ie, HbA1c $> 6.5\%$, or fasting plasma glucose > 126 mg/dL, or classic symptoms of hyperglycemia with random plasma glucose > 200 mg/dL) that cannot be managed by the adjustment of concomitant medications such as insulin and oral hypoglycemic agents.
- Flare or worsening of disease activity, defined as:
 - **Weeks 0 to 11:** DAS28-ESR ≥ 3.2 and increase of > 0.6 from the Week 0 assessment sustained over 2 consecutive study visits; **or** DAS28-ESR ≥ 3.2 and increased of > 1 from the Week 0 assessment at a single visit.
 - **Weeks 13 to 23:** DAS28-ESR < 3.2 and increase of 1.2 from the Week 12 assessment; **or** DAS28-ESR ≥ 3.2 and increased of > 0.6 from the Week 12 assessment sustained over 2 consecutive study visits; **or** DAS28-ESR ≥ 3.2 and increase of > 1 from the Week 12 assessment at a single visit.
- Failure to achieve LDA at Week 12.

- Development of any other AE of at least moderate intensity and possibly, probably or definitely related to study drug that cannot be managed by the adjustment of concomitant medications.

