20.3.2 Secondary Efficacy Endpoints

- Proportion of subjects who maintained DAS28-ESR < 3.2 from Week 12 through Week 24.
- Time to disease activity flare from Week 12 through Week 24.
- Proportion of subjects with CDAI \leq 10 at Week 12.
- Proportion of subjects who meet criteria for ACR20 at Week 12.

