20.7 Statistical Power and Sample Size Considerations

It is expected that 360 subjects will be screened and a total of 232 subjects will be enrolled in this study. It is estimated that 55% of subjects will either drop out before Week 12 or will not achieve LDA by Week 12. The remaining 45% of subjects will have achieved LDA after 12 weeks of treatment with Acthar and will be randomized into 2 treatment groups in Part 2 of the study. Based on results from previous studies ([Pincus, 2011](#)) and ([Ruperto et al, 2008](#)), it is estimated that 80% of the Acthar group and 50% of the placebo group will maintain LDA after the 12 additional weeks of treatment. Assuming that 52 subjects per group (104 subjects total) will complete Part 2, and based on the use of a 2-sided, 2-sample comparison of proportions at the $\alpha = 0.05$ level of significance, there will be 90% of power to detect a difference in the 2 treatment groups.

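### Optional: maintained LDA in Part 2 is tested without using Week 12 DAS28-ESR; adjusting for it might add about 0 to 3 points of power, or practically none if only Week 24 counts

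*Combined protocol and SAP*

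**What the plan says.** The only test named in the supplied text for this endpoint is in the synopsis (Statistical Methods, Efficacy): "the proportions of subjects who maintain LDA in Part 2 for the 2 treatment groups will be compared using a 2-sided Pearson's chi-square test", at the 0.05 level. Section 20.3.2 defines the endpoint as "Proportion of subjects who maintained DAS28-ESR < 3.2 from Week 12 through Week 24". Section 20.7 assumes that 80% of the Acthar group and "50% of the placebo group will maintain LDA after the 12 additional weeks of treatment", with 52 completers per group and 90% power.

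The Week 12 score decides entry to Part 2. Section 9.3 states: "Subjects who have achieved LDA, defined as DAS28-ESR < 3.2, will enter a double-blind randomized maintenance period". The Week 12 visit list in Section 14.4 includes "Contact IXRS and confirm disease activity eligibility", and Section 15.1 says that "components of the DAS28-ESR (swollen joint count, tender joint count, ESR, General Health VAS) will be entered" into IXRS, which calculates the score. Section 11.1 gives 1:1 randomisation. No covariate or stratification factor appears in the supplied text.

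Two further rules bear on how well the Week 12 score can predict the outcome. Section 11.1 says "Subjects who experience a flare in disease activity will be discontinued from the study", and for Weeks 13 to 23 flare is measured as a rise from Week 12. One of its clauses in Section 15.3.1 is "DAS28-ESR < 3.2 and increase of 1.2 from the Week 12 assessment".

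**The concern.** The outcome is DAS28-ESR against a 3.2 cut-off, and each randomised subject already has a value on that scale, measured before randomised treatment. A covariate of this kind can tighten the treatment comparison with no new data and essentially no missing values. An unadjusted test forgoes whatever it offers. The endpoint is secondary, and study success rests on the Part 1 response rate, so what is at stake is precision in the randomised comparison and not the trial's formal outcome.

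**Working it through.** **1. The plan's own figure.** Inputs from Section 20.7: n = 52 per group, rates 0.80 and 0.50, two-sided alpha 0.05.

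- Pooled rate = 0.65. SE under the null = sqrt(2 x 0.65 x 0.35 / 52) = 0.0935.
- SE under the alternative = sqrt((0.80 x 0.20 + 0.50 x 0.50) / 52) = 0.0888.
- z = (0.30 - 1.96 x 0.0935) / 0.0888 = 1.31, so power = 90.6%. Exact enumeration of the Pearson test gives 91.0%.

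The stated 90% reproduces.

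**2. What a given prognostic strength would buy.** If Week 12 DAS28-ESR explains a share R2 of the within-group outcome variance, the effective size is about 52 / (1 - R2) per group:

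- R2 = 0: 90.6%, gain 0.0 points
- R2 = 0.02: 91.1%, gain 0.6
- R2 = 0.05: 92.0%, gain 1.4
- R2 = 0.10: 93.3%, gain 2.7
- R2 = 0.12: 93.8%, gain 3.2

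The documents give no R2.

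**3. Why R2 could be low.** Two forces oppose each other. A subject just below 3.2 has little room before losing LDA. But flare in Weeks 13 to 23 is a rise from Week 12, and regression to the mean makes such rises likelier in subjects with a low Week 12 score.

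**4. Simulation with the flare rules applied.** All of the following are assumptions:

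- Between-subject SD 0.6-0.8, visit SD 0.4-0.6, drift SD 0.5-1.0 (8 combinations).
- Mean Week 12 score 3.3 before selection, and randomisation if the observed score is below 3.2. Total SD runs from sqrt(0.36 + 0.16) = 0.72 to sqrt(0.64 + 0.36) = 1.0. The share randomised is therefore Phi(-0.14) = 44% to Phi(-0.10) = 46%, in line with the plan's 45%.
- Linear drift calibrated to 80% and 50% maintained; all three flare clauses applied at Weeks 16 and 20; flare counted as not maintained.
- Adjusted test: score test for treatment in a logistic model with continuous Week 12 DAS28-ESR. Without the covariate this is the Pearson test, so the form of the test does not contribute to the difference.

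Results, 10,000 trials per setting:

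- LDA at Weeks 16, 20 and 24: AUC of the Week 12 score 0.59-0.74; Pearson 90.9-91.5%; adjusted 91.4-94.7%; gain 0.2 to 3.4 points; precision equal to 52-59 per group.
- LDA at Week 24 only: AUC 0.46-0.66; Pearson 90.4-91.2%; adjusted 90.3-92.1%; change -0.3 to +1.1 points; precision equal to 51-54 per group.

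Extreme settings in 40,000 paired trials: every visit, 90.7% to 90.9% (+0.2) and 90.9% to 94.1% (+3.2); Week 24, 91.3% to 91.2% (-0.1) and 90.9% to 92.0% (+1.1). A repeat with 6,000 trials per setting gave +0.2 to +3.4 and -0.5 to +1.2 points.

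The mean width of the 95% interval for the risk difference falls from 0.348 to 0.324-0.345 (every visit) or to 0.338-0.347 (Week 24).

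**5. Sensitivity to how flare is counted.** If a flare withdrawal keeps its status at the withdrawal visit, the gains are 0.9 to 4.2 points (every visit) and 0.0 to 2.6 (Week 24). If flare withdrawals are ignored, they are 0.4 to 3.8 and 0.5 to 3.2.

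**6. Downside.** With a non-prognostic score, power was 90.5% adjusted against 90.8% for Pearson, a loss of 0.3 points. A logistic Wald test lost 0.4 (91.1% to 90.7%). Type I error at 65% in both groups was 5.0-5.4% for the adjusted score test, 5.1-5.4% for Pearson and 5.2-5.8% for the corrected robust Wald test.

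**The case against.** The strongest reply is that nothing needs repair. The Pearson test is valid under randomisation, matches the two-proportion basis of the sample size, and meets the planned power. That stands, and it is why the change is optional. A reader might infer from the missing covariate that the planned test is wrong or the comparison underpowered. The documents support neither.

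The gain rests on assumed SDs. This also stands: a between-subject SD of 1.0, outside the range used, gave +4.1 points at every visit, and most settings inside the range gave much less than 3. To reach 80% and 50%, the model also needs randomised Acthar subjects to improve by a further 0.2-1.9 units on average, which the documents neither support nor exclude. A reader might take 3 points as the expected gain. It is the upper end, under one reading of the endpoint.

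A covariate rule may already exist. Section 20.1 and Sections 20.4 and 20.5 are listed in the contents but are not in the supplied text, and Section 20.3.7 shows two sentences that name no test. So the absence of adjustment is established only for the text that can be seen.

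Finally, if adjustment is only supportive, the main test gains nothing. That is correct, and limits what may be claimed for that route. It does not defeat adjustment as the main analysis.

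**Conclusion.** The point holds as an optional efficiency gain. The synopsis test leaves unused a value that is held for every randomised subject before Part 2 treatment starts. With flare counted as not maintained and the SDs assumed above, adjusting for it is worth about 0 to 3 points of power if LDA is required at every visit, which is the plainer reading of Section 20.3.2. If only Week 24 counts, it is worth about -0.5 to +1 point, practically nil. The loss if the score is not prognostic is at most about half a point.

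The result does not carry over to time to flare, which was not examined. Which reading of maintained applies, and how flare withdrawals are counted in the analysis, is a separate matter of endpoint definition. It governs the size of the gain but adds no weight to the case for a covariate.

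**What to change.** Before unblinding, prespecify as the main analysis of maintained LDA a logistic model with treatment and continuous Week 12 DAS28-ESR, and test treatment with the score test from that model. Report the standardised (marginal) risk difference with a small-sample-corrected robust 95% interval, so that the effect stays a difference in proportions and is not replaced by a conditional odds ratio. State that the score test decides, because it and the interval can disagree at the margin. Keep the Pearson test as supportive and leave the log-rank test for time to flare unchanged.

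This needs no new data, visits or IXRS change. Because Section 24 requires an amendment for a change of plan, and the gain may be nil, include it in the next amendment and do not raise one for this alone. If adjustment is added only as a supportive analysis, claim no power gain for the main test. If a covariate rule already exists in text not supplied, no change is needed.

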7 STUDY SCHEMATIC AND SCHEDULE OF EVENTS

7.1 Study Schematic

Figure 7-1: Study Overview

7.2 Schedule of Study Events

Table 7-1: Schedule of Study Events

Assessment/Procedure	Screening (Day -28 to Day -1)	Part 1 Open Label Period				Part 2 Randomized Maintenance Period			Unscheduled Visit ^a	Follow-up 28 (± 2) Days After Final Dose of Study Drug
		0/Base- line	4 (± 5 days)	8 (± 5 days)	12 (± 2 days)	16 (± 5 days)	20 (± 5 days)	24 (± 5 days) /Early Termination		
Week										
Informed Consent	X									
Inclusion/Exclusion Criteria Review	X	X								
Medical/Surgical History	X									
Current Medical Condition Review		X	X	X	X	X	X	X	X	X
Demographics	X									
Complete Physical Examination	X							X		
Limited Physical Examination		X	X	X	X	X	X		X	X
28 Joint Count	X	X	X	X	X	X	X	X		
Height and Weight ^b	X	X	X	X	X	X	X	X	X	X
Vital Signs ^c	X	X	X	X	X	X	X	X	X	X
Clinical Laboratory Tests ^d	X	X	X	X	X	X	X	X		X
HbA1c	X				X			X		
ESR and CRP	X	X	X	X	X	X	X	X		
Serum Pregnancy Test	X							X		
Urine Pregnancy Test		X	X	X	X	X	X			X
Hepatitis Serology	X									
IGRA for TB	X									
		X			X			X		
		X			X			X		
General Health VAS	X	X	X	X	X	X	X	X		
Patient Assessment of Pain (VAS)		X	X	X	X	X	X	X		
Patient Global Assessment of Disease Activity (VAS)		X	X	X	X	X	X	X		
Physician Global Assessment of Disease Activity (VAS)		X	X	X	X	X	X	X		

Assessment/Procedure	Screening (Day-28 to Day -1)	Part 1 Open Label Period				Part 2 Randomized Maintenance Period			Unscheduled Visit ^a Follow-up 28 (± 2) Days After Final Dose of Study Drug
		0/Base- line	4 (± 5 days)	8 (± 5 days)	12 (± 2 days)	16 (± 5 days)	20 (± 5 days)	24 (± 5 days) /Early Termination	
HAQ-DI		X	X	X	X	X	X	X	
FACIT-F		X	X	X	X	X	X	X	
WPAI		X	X	X	X	X	X	X	
Hospital Admissions, ED and Nonstudy Outpatient Visits			X	X	X	X	X	X	
IXRS Contact	X	X	X	X	X	X	X		
Discontinue Subjects Who Have Not Achieved LDA, Randomize Subjects With LDA					X				
Study Drug and Diary Training		X							
Study Drug Accountability			X	X	X	X	X	X	
Dispense Study Drug		X	X	X	X	X	X		
Administer First Dose ^e		X							
Diary Review			X	X	X	X	X	X	
Adverse Events and Concomitant Treatments						X			

^aChecked assessments are required at any unscheduled visit. Additional assessments may be done at the investigator's discretion.

^bHeight is required at screening only.

^c Blood pressure, pulse rate, respiratory rate and body temperature. Blood pressure will be measured in triplicate at the Screening and Baseline Visits

^dChemistry, hematology, urinalysis.

^eThe first dose will be administered clinic and the subject will be observed for at least 1 hour after dosing.

8 ETHICAL CONSIDERATIONS

This clinical study is designed to comply with ICH Guidance on General Considerations for Clinical Trials and applicable national and local regulations.

8.1 Institutional Review Board/Independent Ethics Committee

It is the responsibility of the investigator to obtain the approval of the IRB/IEC before the start of the study. The investigator will provide Mallinckrodt with a statement of compliance from the IRB/IEC and/or the US Department of Health and Human Services general assurance number. A copy of the approval letter along with a roster of IRB/IEC members and compliance letter and/or the US Department of Health and Human Services general assurance number will be retained as part of the study records. During the course of the study, the investigator will provide timely and accurate reports to the IRB/IEC on the progress of the study at appropriate intervals (not to exceed 1 year) and at the completion of the study. The investigator will notify the IRB/IEC of serious adverse events (SAE) or other significant safety findings per IRB/IEC guidelines. The study protocol, informed consent form (ICF), advertisements (if any), and amendments (if any) will be approved by the IRB/IEC in conformance with international, national and local regulatory requirements; and the Code of Federal Regulations (CFR), Title 21, Part 56 (where applicable).

8.2 Ethical Conduct of the Study

The study will be conducted in full compliance with applicable international, national and local regulatory requirements; United States (US) Food and Drug Administration (FDA) regulations including 21 CFR 314.106 and 312.120, (where applicable); and ICH guidelines for good clinical practice (GCP) and in accordance with the ethical principles that have their origins in the Declaration of Helsinki.

8.3 Subject Information and Consent

The ICF must be approved by the sponsor and the IRB/IEC before any subject provides consent. The investigator will provide Mallinckrodt with a copy of the IRB/IEC-approved ICF and a copy of the IRB/IEC's written approval before the start of the study.

At the Screening Visit, subjects will read the ICF and a Health Insurance Portability and Accountability Act (HIPAA) authorization form (if applicable) after being given an explanation of the study. Before signing the ICF and the HIPAA authorization form (if applicable), subjects will have an opportunity to discuss the contents of these forms with study site personnel.

Subjects must assent understanding of and voluntarily sign these forms in compliance with ICH GCP guidelines and 21 CFR, Parts 50 and 312 (where applicable), before participating in any study-related procedures. Subjects will be made aware that they may withdraw from the study at any time. Subjects unable to give written informed consent must orally assent to the procedures, and written informed consent must be obtained from a legally authorized representative in accordance with national and local laws, as applicable.

The ICF must contain all applicable elements of informed consent and the mandatory statements as defined in by national and local regulations including confidentiality. All versions of each subject's signed ICF must be kept on file by the site for possible inspection by regulatory authorities and/or authorized Mallinckrodt personnel. Signed copies of the ICF and the HIPAA authorization form, if applicable, will be given to the subject.

The subjects will be made aware of their right to see and copy their records related to the study for as long as the investigator has possession of this information. If the subject withdraws consent and/or HIPAA authorization, the investigator can no longer disclose health information, unless it is needed to preserve the scientific integrity of the study.

